6.0 ADVERSE EVENT REPORTING

6.1 Adverse Events (AEs) is defined as any unfavorable and unintended sign, symptom, or disease temporally associated with the use of a medical treatment or procedure regardless of whether it is considered related to the medical treatment or procedure (attribution of unrelated, unlikely, possible, probable, or definite). These events will be

recorded for each patient at the specified assessment time points and are subject to review by the investigators and data safety monitoring committee (DSMC).

6.2 Serious Adverse Events (SAEs)

Any adverse event that results with any of the following outcomes:

- Death;
- A life-threatening experience;
- Inpatient hospitalization or prolongation of existing hospitalization;
- A persistent or significant disability/incapacity;
- A congenital anomaly/birth defect; or
- Other medically important events.

6.3 All adverse events will be reported to the PI and co-investigators.

6.4 Any SAE will be reported to the DSMC in a scheduled summary of toxicities and SAEs at 4 months after completed enrollment of the ongoing dose level/before dose escalation.

6.5 Any death thought to be at least possibly related to treatment will halt the study and will be reported to the DSMC within 24 hours of the investigators knowledge of the event.

6.6 The study may also be halted should the PI feel for any reason there is undo risk to patients with continued dose escalation.

7.0 DATA SAFETY MONITORING PLAN

7.1 Data Safety Monitoring Committee (DSMC)

The Winship Cancer Institute Phase I trial unit data safety monitoring committee will monitor this trial. As per WCI policy, the DSMC monitors all investigator initiated studies and cooperative group studies at Winship. Each qualifying study is reviewed at least once a year. Two of the first 5 patients enrolled to investigator-initiated studies and 10% of total accrual is reviewed. Once a chart is monitored, the PI and the study coordinator are presented with the findings. They have a 2 week period to respond to the findings. A summary report is submitted to the DSMC for committee review. Any serious unanticipated problem is reported to the IRB with due notice to the PI.

Included in the DSMC review:

- Regulatory documents
- Patient eligibility
- Informed consent process
- Accuracy and timeliness of data
- Verification of source documents
- Toxicity assessment process

7.2 Scheduled Monitoring

7.2.1 The study PI and co-investigators will meet every month to review enrollment, patient treatments, toxicities and attribution (originally graded by treatment physician), outcomes and categorization of any failures.

7.2.3 Radiation therapy quality assurance

Radiation specifics including simulation, treatment delivery and dose prescription specifications will be approved by treating physician. All treatment plans are routinely reviewed the week of treatment initiation by board certified radiation oncologists from the Emory Department of Radiation Oncology who are not co-investigators on the study. Any protocol violations will be reported to the PI and co-investigators.

- 7.2.4 Every 4 months from the date of first enrollment and/or prior to each dose escalation, a summary of all toxicities ≥ 3 and their graded attributions will be submitted to the DSMC.

APPENDIX B

CTCAE (Common Terminology Criteria for Adverse Events), version 4.03

The exact full criteria for toxicity assessment can be obtained at the NCI CTEP website at the following link:

http://evs.nci.nih.gov/ftp1/CTCAE/CTCAE_4.03_2010-06-14_QuickReference_8.5x11.pdf

APPENDIX C

RECIST Guideline Version 1.1

<http://imaging.cancer.gov/clinicaltrials/imaging>

APPENDIX D

RTOG RPA Classification System

RPA Class I All of the following criteria:
KPS \geq 70%
Age < 65 years
Absence of extracranial metastases
Controlled primary cancer

RPA Class II KPS \geq 70% **and**
One or more of the following criteria:
Age > 65 years
Presence of extracranial metastases
Uncontrolled primary cancer

RPA Class III KPS < 70%

KARNOFSKY PERFORMANCE SCALE

- 100 Normal; no complaints; no evidence of disease
- 90 Able to carry on normal activity; minor signs or symptoms of disease
- 80 Normal activity with effort; some sign or symptoms of disease
- 70 Cares for self; unable to carry on normal activity or do active work
- 60 Requires occasional assistance, but is able to care for most personal needs
- 50 Requires considerable assistance and frequent medical care
- 40 Disabled; requires special care and assistance
- 30 Severely disabled; hospitalization is indicated, although death not imminent
- 20 Very sick; hospitalization necessary; active support treatment is necessary
- 10 Moribund; fatal processes progressing rapidly
- 0 Dead

APPENDIX A – Patient Assessment Timeline

	Baseline	Weekly on RT	1 month	4 months	7 months	10 months	13 months	16 months	19 months	22 months	25 months
H&P	X		X	X	X	X	X	X	X	X	X
Toxicity Assessment		X	X	X	X	X	X	X	X	X	X
MRI	X		X	X	X	X	X	X	X	X	X
HVLT-R	X		X	X	X		X		X		X
MMSE	X		X	X	X		X		X		X
MOS	X		X	X	X		X		X		X
FACT-Br	X		X	X	X		X		X		X
Imaging Response Evaluation			X	X	X	X	X	X	X	X	X

*Assessments may occur within a +/- 3 week window the specified time.

APPENDIX E

Eligibility Checklist

1. _____ Pathological proven diagnosis of solid tumor malignancy, not a radiosensitive or non-solid (eg. small cell lung carcinomas, germ cell tumors, leukemia, or lymphoma) or unknown tumor histology.
2. _____ Age ≥ 18 .
3. _____ One brain metastasis or brain metastasis resection cavity with maximal diameter greater $\geq 3\text{cm}$ (or $\geq 14\text{ cc.}$) and $\leq 6\text{cm}$.
4. _____ RPA class I-II/ Karnofsky Performance Status $\geq 70\%$ (See **Appendix D for definitions**)
5. _____ No Prior SRS to adjacent lesion such that planning target volume would have received more than 5 Gy
7. _____ No concurrent chemotherapy (no chemotherapy starting 14 days before start of radiation).
8. _____ No evidence of leptomeningeal disease by MRI and/or CSF cytology.
9. _____ Negative serum or urine pregnancy test within 4 weeks of enrollment
10. _____ Less than or equal to 8 weeks between resection and enrollment
11. _____ No metastases to brain stem, midbrain, pons, or medulla or within 5 mm of the optic apparatus (*optic nerves and chiasm*).
12. _____ Patient is able to undergo MRI evaluation for treatment planning and follow-up

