Stereotactic Radiosurgery, as defined by the American Society for Therapeutic Radiology and Oncology (ASTRO), the American Association of Neurological Surgeons (AANS), and the Congress of Neurological Surgeons (CNS), includes single dose SRS and well as HR delivered in 2-5 fractions over multiple days¹⁴⁻¹⁵. The majority of data supporting the use of SRS for the treatment of brain metastases has evaluated only single dose SRS and it is unclear whether the same results can be attributed to HR in 2-5 fractions. Brain metastasis amenable to single fraction SRS are typically defined as those measuring less than 3cm and producing less than 1cm of midline shift³. For brain metastasis not amenable to SRS, but for which focal brain radiation is indicated for boost or as salvage after WBRT or for avoidance of neurocognitive decline, HR provides an alternative treatment option. Current data describing the use and results of HR for the treatment of brain metastasis is limited to few retrospective series. Pater and colleagues from University of Cincinnati have demonstrated HR delivered to a dose of 30 Gy in 5 fractions to be effective and tolerable in a series of 34 patients, with a 6% (n=2) incidence of asymptomatic radiation necrosis and a 6 month actuarial local control rate of 68%¹⁶. A second series of 43 patients with metastatic breast cancer treated at Staten Island University Hospital utilized HR to a dose of 24 Gy delivered in 4 fractions, with a median survival from treatment of 7.5 months¹⁷. Recently, Wang et al. have reported on the use of HR in the setting of resected brain metastasis with resection cavities > 3cm and have demonstrated a local control rate of 80% at 6 months with the use of 24 Gy in 3 daily fraction¹⁸. With only a few series reported, the optimal dose and fractionation schedule is unknown.

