3.4.6 Dose Limitation to Critical Structures

1. In addition to the above defined GTVs, CTVs and PTVs, both eyes, the lenses of both eyes, the optic nerves, the optic chiasm, the brainstem and the spinal cord and the whole brain and normal brain parenchyma will be contoured. Normal brain is defined as the whole brain minus the GTV. Dose-volume histograms will be generated and whole organ dose and maximum point dose will be recorded for each critical structure.
2. If the patient has received no prior cranial irradiation, the maximal point doses permissible to the structures from the current radiation therapy plan are listed below* (Table 2).

3. If the patient has received previous WBRT, the previous dose received to critical structures should be obtained or a representative dose distribution file should be simulated. This dose should then be converted to BED (assuming an alpha-beta ratio of 3 for late effects) and added to the BED to the critical structures from the current treatment plan. This sum BED must meet the cumulative dose constraint below[¶] (Table 2). No adjustments for time between previous radiation treatment will be made for the purpose of this protocol.
4. If a patient is recommended to receive whole brain radiation after completion of the study treatment, the constraints listed in Table 3 should be met during the whole brain radiation treatment. It is recommended that the 90% isodose volume from the hypofractionated radiosurgery treatment be created into an avoidance structure and constrained such that the maximum dose to this structure or the normal brain has a cumulative BED₃ of ≤ 150 (equivalent to max dose 15-18 Gy when delivered in 3-3.5 Gy per fraction).

Table 2. Normal Tissue Constraints for Hypofractionated Radiosurgery Treatment

Cumulative BED ₃	Volume	No Previous RT*	Previous RT [¶]
		Maximum Dose	Maximum Cumulative BED ₃
Brainstem	Max, $\leq 0.03\text{cc}$	26 Gy	90
Spinal Cord	Max, $\leq 0.03\text{cc}$	22 Gy	75
Eye (Globe), each	Max, $\leq 0.03\text{cc}$	20 Gy	66
Lens, each	Max, $\leq 0.03\text{cc}$	2.5	12
Optic Nerve, each	Max, $\leq 0.03\text{cc}$	26 Gy	90
Optic Chiasm	Max, $\leq 0.03\text{cc}$	26 Gy	90
Normal Brain	Modal	20 Gy	15 Gy
Normal Brain	$\leq 23\text{ cc}$	4 Gy/fraction	4Gy/fraction

Table 3: Constraints for Whole Brain Radiation following hypofractionated radiosurgery

Cumulative BED ₃	Volume	WBRT after study treatment
		Maximum Cumulative BED ₃
Brainstem	Max, $\leq 0.03\text{cc}$	90

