Spinal Cord	Max, $\leq 0.03\text{cc}$	75
Eye (Globe), each	Max, $\leq 0.03\text{cc}$	66
Lens, each	Max, $\leq 0.03\text{cc}$	12
Optic Nerve, each	Max, $\leq 0.03\text{cc}$	90
Optic Chiasm	Max, $\leq 0.03\text{cc}$	90
Dose within 90% isodose line from study treatment or within normal brain	Max, $\leq 0.03\text{cc}$	150

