4.2 Exclusion Criteria

- 4.2.1 Prior SRS to adjacent lesion such that planning target volume would have received more than 12 Gy
- 4.2.2 RPA class III (KPS < 70%, see **Appendix D definitions**).
- 4.2.3 Brain metastasis or resection cavity volume < 3 cm or 14 cc. or > 6cm or 113 cc.
- 4.2.4 Radiosensitive or non-solid (eg. small cell lung carcinomas, germ cell tumors, leukemias, or lymphomas) or unknown tumor histologies.
- 4.2.5 Concurrent chemotherapy (no chemotherapy starting 14 days before start of radiation).
- 4.2.6 Evidence of leptomeningeal disease by MRI and/or CSF cytology.
- 4.2.7 Current pregnancy
- 4.2.8 More than 8 weeks between resection and radiosurgical procedure
- 4.2.9 Metastases to brain stem, midbrain, pons, or medulla or within 5 mm of the optic apparatus (*optic nerves and chiasm*).
- 4.2.10 Inability to undergo MRI evaluation for treatment planning and follow-up

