4.4 Recruitment Plan

Patients with brain metastases who are referred to Emory Radiation Oncology for brain radiotherapy either in the setting of intact solid metastatic tumor(s) or after resection of the metastatic tumor(s) will be considered for this study. All Emory radiation oncology physicians will be made aware of the trial, including main objectives and patient eligibility. Once the trial is open to accrual it will be up to the primary radiation oncologist to screen patients for eligibility, explain the risk and benefits of trial participation, and inform patients of the alternative treatment options off of study. Copies of this study protocol and eligibility checklist (**Appendix E**), study consents (**Appendix F and G**) and initial assessment form (**Appendix H**) will be made available to all physicians in the radiation oncology department at Emory University Hospital and Emory University Hospital Midtown.

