5.3 Statistical Analysis

5.3.1 Primary Analysis: The rate of toxicities at 4 months will be calculated with 95% confidence interval (CI).

5.3.2 Secondary Analysis:

5.3.2.1 The median time to local/distant brain progression will be calculated by Kaplan-Meier method with 95% CI. For a given time point, say 4 month, the rate of local/distant progression will be calculated with 95%CI.

5.3.2.2 The median of OS time with 95% CI will be calculated by Kaplan-Meier method.

5.3.2.3 Neurocognitive effect and QOL outcomes will be regressed over time using GEE model. The population change over time (slope) will be estimated with 95%CI.

5.3.3 Patient Stratification: All enrolled patients will proceed through dose escalation as a single cohort, however patients will be analyzed as separate strata, should enrollment allow it, based on the following criteria.

5.3.3.1 Intact brain metastasis versus resection cavity.

5.3.3.2 No previous cranial irradiation versus previous WBRT or other cranial irradiation.

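### Section 4.2.1 sets the prior-SRS exclusion at 12 Gy, the eligibility checklist sets it at 5 Gy, and no text says which governs

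*Combined protocol and SAP*

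**What the plan says.** **Prior SRS.** Section 4.2.1 of the protocol lists as an exclusion "Prior SRS to adjacent lesion such that planning target volume would have received more than 12 Gy". Item 5 of the Appendix E checklist requires "No Prior SRS to adjacent lesion such that planning target volume would have received more than 5 Gy". Apart from the number and the leading negative, the wording is the same. Section 4.4 leaves screening to the primary radiation oncologist and makes "Copies of this study protocol and eligibility checklist" available to radiation oncology physicians at both hospitals. Previously irradiated patients may be enrolled: section 5.3.3.2 plans a stratified analysis of "No previous cranial irradiation versus previous WBRT or other cranial irradiation".

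**Cumulative dose.** The summation rule in 3.4.6 item 3 begins "If the patient has received previous WBRT, the previous dose received to critical structures should be obtained". It is written for earlier WBRT and for critical structures.

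**WBRT after study treatment.** Section 3.4.6 item 4 recommends holding the cumulative BED3 at or below 150 and adds that this is "equivalent to max dose 15-18 Gy when delivered in 3-3.5 Gy per fraction". No dose level is named. Table 3 repeats the 150 limit in the row "Dose within 90% isodose line from study treatment or within normal brain".

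**The concern.** Two physicians screening the same patient could reach opposite answers, each following an official page. If 5 Gy is the intended limit, 4.2.1 admits patients who should be kept out. If 12 Gy is intended, the checklist turns away eligible patients. In a dose-finding trial with cohorts of 3, where a DLT is CNS toxicity of grade 3 or higher at least possibly due to radiation, the amount of earlier dose allowed in the target should be defined once.

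The WBRT bracket raises a smaller problem of the same kind. One fixed dose range is called equivalent to a cumulative cap, although the study dose that counts toward the cap changes with every level.

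**Working it through.** **1. The eligibility conflict.** This is a comparison of texts.

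| Earlier SRS dose to the PTV | Section 4.2.1 | Checklist item 5 |
|---|---|---|
| up to 5 Gy | eligible | eligible |
| more than 5, up to 12 Gy | eligible | not eligible |
| more than 12 Gy | not eligible | not eligible |

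Only the middle row conflicts. Anyone who passes the checklist also passes 4.2.1, so the 5 Gy limit satisfies both texts.

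For scale, the two limits can be put on the protocol's late-effect measure, BED3 = D(1 + d/3), where D is total dose and d is dose per fraction. The alpha-beta ratio of 3 is from 3.4.6 item 3. The number of earlier fractions is an assumption; section 1.0 takes SRS to include "single dose SRS and well as HR delivered in 2-5 fractions", so both ends are shown.

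- One fraction: 5(1 + 5/3) = 13.3 against 12(1 + 12/3) = 60.0.
- Five fractions: 5(1 + 1/3) = 6.7 against 12(1 + 2.4/3) = 21.6.

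**2. The WBRT bracket.** Inputs are the Table 1 doses in 5 fractions, the cap of 150, and WBRT of 15-18 Gy at 3-3.5 Gy per fraction.

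The same formula reproduces Table 1's BED3 column at every level after rounding (78, 90, 103, 117, 131, 147). The bracket adds between 15(1 + 3/3) = 30.0 and 18(1 + 3.5/3) = 39.0. The study dose may then use 111 to 120. The WBRT dose that fits is the remainder under 150 divided by 2.167 (3.5 Gy fractions) or by 2 (3 Gy fractions). With the study dose counted at prescription:

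| Level | Study BED3 | Left under 150 | WBRT that fits (Gy) | Total with 15-18 Gy |
|---|---|---|---|---|
| -1 | 77.9 | 72.1 | 33.3-36.0 | 107.9-116.9 |
| 0 | 90.0 | 60.0 | 27.7-30.0 | 120.0-129.0 |
| 1 | 102.9 | 47.1 | 21.7-23.5 | 132.9-141.9 |
| 2 | 116.7 | 33.3 | 15.4-16.7 | 146.7-155.7 |
| 3 | 131.3 | 18.8 | 8.7-9.4 | 161.3-170.3 |
| 4 | 146.7 | 3.3 | 1.5-1.7 | 176.7-185.7 |

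The bracket matches the cap only near level 2. It is stricter than the cap below that level and over the cap above it.

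The text does not say at what dose the study contribution is counted. At 90% of prescription, level 3 gives 33.75(1 + 6.75/3) = 109.7, so totals are 139.7-148.7 and within the cap. Level 4 gives 36(1 + 7.2/3) = 122.4, so totals are 152.4-161.4 and still over. This reading is the weaker one, because the cap is set on a maximum dose.

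**The case against.** **The protocol body governs.** Section 3.1 ties enrolment to criteria listed in the body, and the checklist is the looser text elsewhere: it omits the 113 cc upper limit and counts the 8 weeks after resection to enrolment instead of to radiosurgery. This hints that 12 Gy is the reference. It does not settle the matter, because 3.1 names only inclusion criteria and no text ranks the two pages.

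**The practical effect may be small.** This stands. The checklist is the safer of the two, section 4.1.3 requires one brain metastasis, and the 5.3.3.2 stratum does not single out earlier SRS to a neighbouring lesion.

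**Other limits may cover the same tissue.** A reader might infer that this threshold is the only protection for a previously irradiated PTV. That goes too far. Table 2 has a column for previous RT with normal-brain rows, and normal brain is defined as whole brain minus GTV, so it takes in the PTV rim outside the GTV. Table 2 still gives no limit for the PTV as a whole, and the text of item 3 is confined to WBRT.

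**The WBRT bracket hardly matters.** Largely accepted. It sits in a recommendation, WBRT takes the patient off study (4.6.2), and Table 3 supplies the working limit. In addition, 18 Gy is not a whole number of 3.5 Gy fractions. With five fractions the upper end is 17.5 Gy, or BED3 37.9, which lowers the upper totals by about 1 and changes no conclusion.

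**The study plan alone might break the cap.** From the 80% and 50% prescription isodose lines for dynamic conformal arcs and Gamma Knife, a reader might infer that maximum doses exceed BED3 150 before any WBRT. That inference leaves out 3.4.4 item 3, which asks for inhomogeneity within 10% of prescription inside the PTV. How that requirement fits with those isodose lines is a separate question and is not part of this point.

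**Conclusion.** The contradiction is real and should be fixed: 12 Gy in 4.2.1, 5 Gy in checklist item 5, with the range above 5 and up to 12 Gy decided by the page consulted. The documents do not show which figure is right. The safety concern is conditional on 5 Gy being intended and 4.2.1 being used alone. The documents give no count of affected patients, and the BED3 contrast depends on an assumed number of earlier fractions.

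A reader might go on to infer that unsuitable patients will be treated or that the MTD will be distorted. Nothing in the documents supports that: the checklist in use may already apply the stricter limit, and neither the EWOC design nor the sample size of 24 depends on this threshold.

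The WBRT bracket is a minor error. Counted at prescription dose it agrees with the cap only near level 2 and exceeds it at levels 3 and 4; counted at 90% of prescription, only level 4 exceeds it. No effect on the MTD is claimed.

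**What to change.** Amend 4.2.1 and Appendix E item 5 to a single threshold chosen by the investigators. Until that is settled, apply 5 Gy. This is a precaution, not a judgement that 5 Gy is correct. If 5 Gy is confirmed, re-check any enrolled patient whose PTV had received more than 5 and up to 12 Gy. If 12 Gy is confirmed, correct the checklist; no re-check is needed.

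In the same amendment, delete the 15-18 Gy bracket from 3.4.6 item 4, rely on the Table 3 cumulative BED3 limit worked out for each patient, and state at what dose the study contribution is counted.

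The cost is one protocol and checklist amendment, possibly a short eligibility re-check, and no extra patients.
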